**1. Background and Rationale**

Ureterorenoscopy (URS) is widely used in the management of ureteral stones due to its high success rates and favorable safety profile. Technological advancements have enabled the use of thin-caliber ureteroscopes, which may facilitate atraumatic ureteral access and reduce the need for dilation. However, the impact of ureteroscope diameter on technical outcomes and surgeon-related factors such as procedural difficulty and intraoperative stress remains unclear.

In addition to traditional surgical outcomes, the psychological burden experienced by the surgeon during technically demanding procedures has gained increasing attention. Therefore, this study aims to evaluate both technical and surgeon-related outcomes associated with different ureteroscope calibers.

---

**2. Objectives****Primary Objective**

To evaluate the impact of ureterorenoscope diameter on intraoperative surgeon stress during ureterorenoscopy.

**Secondary Objectives**

- To compare technical outcomes between thin-caliber and standard-caliber ureteroscopes
- To evaluate procedural difficulty
- To assess perioperative outcomes including:
  - Stone-free rate (SFR)
  - Ureteral injury (Traxer classification)
  - Balloon dilation requirement
  - JJ stent placement
  - Postoperative complications (Clavien–Dindo classification)

### **3. Study Design**

This study was designed as a **prospective, randomized, single-center clinical trial**. The study was approved by the local ethics committee (Decision No: 14, Protocol No: 2025/74) and prospectively registered at ClinicalTrials.gov (Identifier: NCT06935500). Participants were enrolled between March 2025 and December 2025 and randomly assigned in a 1:1 ratio using a simple randomization method.

### **4. Study Population**

#### **Inclusion Criteria**

- Patients scheduled for ureterorenoscopy due to ureteral stones
- Age  $\geq 18$  years
- Provision of written informed consent

#### **Exclusion Criteria**

- Emergency surgery
  - Bilateral ureteral stones
  - Pre-existing double-J stent
  - Radiolucent stones not adequately evaluated on imaging
- 

## **5. Interventions**

Participants were randomized into two groups:

- **Group 1:** 4.5–6.5 Fr semirigid ureteroscope (thin-caliber)
- **Group 2:** 8–9.8 Fr semirigid ureteroscope (standard-caliber)

All procedures were performed under spinal anesthesia using a holmium:YAG laser system. Ureteral dilation and JJ stent placement were performed when clinically indicated.

## **6. Outcome Measures**

### **Primary Outcome**

- Occurrence of stress-related procedures (defined as  $\Delta\text{STAI-TX1} > 0$ )

### **Secondary Outcomes**

- Stone-free rate at 1 month
- Operative time
- Balloon dilation requirement
- Ureteral injury (Traxer classification)
- JJ stent placement

- Postoperative complications (Clavien–Dindo classification)

## **7. Assessment of Surgeon Stress**

Surgeon stress was assessed using the **State–Trait Anxiety Inventory (STAI-TX1)**. The 20-item state anxiety scale was administered immediately before and after each procedure by an independent investigator. An increase in postoperative STAI-TX1 score compared to preoperative score ( $\Delta\text{STAI-TX1} > 0$ ) was defined as a stress-related procedure.

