## **8. Data Collection**

Collected variables included:

- Demographics (age, sex, BMI)
- Stone characteristics (size, location, side)
- Operative time
- Perioperative outcomes
- STAI-TX1 scores

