## **9. Statistical Analysis (SAP)**

Statistical analyses were performed using SPSS (version 20.0; IBM, Armonk, NY).

- Continuous variables: Student's t-test or Mann–Whitney U test
- Categorical variables: Chi-square or Fisher's Exact test
- Significance level:  $p < 0.05$

Sample size was calculated using G\*Power (v3.1). Based on prior SFR data, 65 patients per group were required (power 95%, alpha 0.05). Multivariable logistic regression analysis was performed to identify independent predictors of stress-related procedures.

Variables included:

- Ureteroscope caliber
- Stone size
- Stone location
- Operative time

Adjusted odds ratios (aOR) with 95% confidence intervals were calculated. Model calibration was assessed using the Hosmer–Lemeshow test.

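### Surgeon stress is scored repeatedly on the same operator(s) but modelled without a surgeon or case-order term, which costs power, leaves the non-randomized predictors open to confounding, and limits the conclusion to the participating surgeons

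*Combined protocol and SAP*

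**What the plan says.** Section 6 gives the primary outcome as "Occurrence of stress-related procedures", meaning a STAI-TX1 score that is higher after the procedure than before it. Section 7 makes the surgeon the respondent at every operation: "The 20-item state anxiety scale was administered immediately before and after each procedure by an independent investigator".

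Section 3 describes a "prospective, randomized, single-center clinical trial" in which participants were "randomly assigned in a 1:1 ratio using a simple randomization method". No stratification by surgeon is mentioned, and the number and experience of the surgeons are not given anywhere.

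Section 9 names two analyses that apply to this binary outcome. One is the simple comparison ("Categorical variables: Chi-square or Fisher"'s exact test). The other is a model: "Multivariable logistic regression analysis was performed to identify independent predictors of stress-related procedures". Its terms are caliber, stone size, stone location and operative time, reported as adjusted odds ratios with 95% confidence intervals. No surgeon term, case-order term, random effect or clustered error is named.

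Section 8 opens with "Collected variables included" and lists demographics, stone characteristics, operative time, perioperative outcomes and STAI-TX1 scores. Surgeon and procedure sequence are not on the list.

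**The concern.** The patient is the unit of randomization, but the person measured is the surgeon. The same few people fill in the questionnaire many times. They may differ in how readily a procedure raises their score, and they may change with repetition. An analysis with no surgeon or case-order term discards information that bears directly on the outcome.

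Three things are at stake: the power of the caliber comparison, the credibility of the other odds ratios that the model presents as independent predictors, and the population of surgeons to whom the result applies.

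**Working it through.** **Inputs.** From the documents: 65 per group (130 in total), alpha 0.05, individual 1:1 simple randomization, one center, and the four model terms. Not in the documents, so assumed over a range: 1–5 surgeons, the spread between surgeons, and a stress rate near 40% (logit −0.4).

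**1. The plan's own figure.** The plan states: "Based on prior SFR data, 65 patients per group were required (power 95%, alpha 0.05". The two stone-free rates are not given, so the figure cannot be reproduced, only shown to be attainable. The formula is n = [1.960·√(2p̄q̄) + 1.645·√(p₁q₁ + p₂q₂)]² / (p₂ − p₁)². For 0.61 vs 0.88, p̄ = 0.745 and n = (1.960 × 0.6164 + 1.645 × 0.5861)² / 0.27² = 4.718 / 0.0729 = 64.7, which rounds up to 65. This calculation concerns stone-free rate, not stress. On the stress outcome, 65 per arm gives 80% power for a difference of about 22–24 points (reference rates 20–60%, procedures independent).

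**2. Is the caliber comparison valid without a surgeon term?** I simulated 130 procedures with no caliber effect and tested them with a two-proportion z test (equivalent to chi-square), using 20,000 runs per scenario. Surgeon intercept SDs of 0.605 and 1.187 correspond to latent ICCs of 0.605²/(0.605² + 3.290) = 0.10 and 1.187²/(1.187² + 3.290) = 0.30.

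| Scenario, 1–5 surgeons | Type I error (nominal 5%) |
|---|---|
| Surgeons differ in level, ICC 0.1 or 0.3 | 4.7–5.3% |
| Serial correlation 0.8 between consecutive cases | 4.9–5.2% |
| Linear case-order trend | 4.9–5.1% |

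With 2 surgeons and ICC 0.1, the mean standard error was 0.084 and the empirical SD of the difference 0.085. The comparison is valid because each surgeon uses both calibers by random assignment, so surgeon level and time trend are balanced on average.

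**3. Power lost** (true log-odds ratio 1, 2–5 surgeons).

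| Between-surgeon SD (logit) | No surgeon term | With surgeon term | Gain |
|---|---|---|---|
| 0.5 | 74.6–76.5% | 75.7–77.3% | about 1–2 points |
| 1.0–1.5 | 54–70% | 63–74% | about 4–9 points |

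With one surgeon the gain from a surgeon term is zero.

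**4. Non-randomized predictors.** Operative time was given no true effect, and surgeons were allowed to differ both in typical operative time and in stress propensity. With so few surgeons, these two surgeon-level quantities line up by chance, and the model reads that as an effect of operative time. With 15% of operative-time variance between surgeons, it was declared significant in about 10–15% of trials; a surgeon term brought this to about 5–6%. Over 10–20% of variance the uncorrected range was 9–23%. The inflation shrinks as surgeons become more alike. Stone size and location have the same exposure if case mix differs by surgeon or drifts over time; that was not simulated.

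**5. A caliber effect that varies between surgeons.** The average effect over all surgeons is zero, and the rejection rate is read as a claim about surgeons in general.

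| Slope SD (logit) | 1 surgeon | 2 | 3 | 5 |
|---|---|---|---|---|
| 0.25 | 10.1% | 7.4% | 6.7% | 5.7% |
| 0.5 | 23.7% | 14.7% | 11.1% | 8.8% |
| 1.0 | 47.6% | 31.6% | 24.7% | 17.6% |

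A surgeon fixed effect does not repair this. In a separate run at slope SD 0.5, the rates without and with it were 13.9–14.3% vs 14.1–14.3% (2 surgeons), 10.5–11.3% vs 11.7% (3) and 7.7–9.1% vs 9.2–10.3% (5). Only a narrower conclusion deals with it.

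**The case against.** A reader might infer that repeated measurement makes the confidence interval for caliber wrong, or that the effective sample size is the number of surgeons. The usual cluster formula would suggest so: with 2 surgeons, 65 procedures each and ICC 0.1, 1 + 64 × 0.1 = 7.4, and 130/7.4 = 17.6. The documents do not support that reading. The formula is for treatments assigned to whole clusters; here caliber is assigned patient by patient, and step 2 shows type I error at its nominal level. This part of the defense stands in full, provided that the choice of surgeon did not depend on the allocated caliber and that stress did not carry over from one case to the next.

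The defense has four further arguments.

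- Omitting a prognostic covariate from a randomized comparison is an efficiency choice, not an error. That is right for caliber, but it does not extend to the three non-randomized terms.
- The before-after difference already removes additive differences in anxiety level. True, but it does not remove differences in how often a surgeon's score rises, which is what the binary outcome records.
- The variable list may not be exhaustive. That also stands: absence from the list does not prove that the surgeon went unrecorded. Even so, no listed analysis uses the surgeon.
- Inference to all surgeons is not claimed. The objective indeed names no surgeon population, so step 5 is a limit on what may be concluded, not a demonstrated error.

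**Conclusion.** The point holds as a gap in the model and in the scope of the conclusion. It is not a finding that the caliber test is invalid.

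The repeated measurement on the surgeon and the missing surgeon and case-order terms are plain from Sections 6, 7 and 9. The cost for caliber is power: negligible if surgeons are alike, and up to about 9 points if they differ strongly. For operative time, roughly a doubling or tripling of the 5% false-positive rate is plausible under step 4's assumptions, and here the reported odds ratio and interval can mislead. For generalization, the trial gives no basis beyond its own surgeons if the caliber effect varies between them; with one surgeon that variation cannot even be estimated.

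All these sizes rest on an assumed number of surgeons and assumed spreads. Confidence is medium for that reason.

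**What to change.** - State how many surgeons operated and their experience.
- Retrieve the operating surgeon and the procedure sequence from the operative records.
- Add surgeon, as a fixed effect, and case order to the Section 9 logistic model. Because Section 9 is written in the past tense, say whether these terms were added after the data were analyzed.
- Show the caliber effect separately by surgeon as a descriptive check.
- Word the conclusion as applying to the participating surgeon(s).
- If there was one surgeon, include case order only and state that the result describes that operator.

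The cost is a small retrieval from existing records, assuming they hold this information, and a few degrees of freedom (for 2–5 surgeons, 1–4 for surgeon plus 1 for a linear case-order term). The conclusion also becomes narrower. Nothing in the conduct of the procedures changes.

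### The primary outcome keeps only the sign of the STAI-TX1 change, and no analysis of the numeric scores is named to support it

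*Combined protocol and SAP*

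**What the plan says.** Section 6 (Primary Outcome) names "Occurrence of stress-related procedures", defined as a STAI-TX1 change greater than 0. Section 7 repeats the rule: "An increase in postoperative STAI-TX1 score compared to preoperative score" makes a procedure stress-related. Neither section gives a minimum important change, an allowance for measurement error or a reason for the cut at 0.

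The underlying data are numeric. Section 7 says "The 20-item state anxiety scale was administered immediately before and after each procedure by an independent investigator", and Section 8 lists "STAI-TX1 scores" among the collected variables.

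The secondary outcomes in Section 6 include no numeric STAI measure. In Section 9 the binary outcome falls under "Categorical variables: Chi-square or Fisher's Exact test" and is also the response in a multivariable logistic regression on caliber, stone size, stone location and operative time. The pre-procedure STAI-TX1 score is not among those covariates. Section 9 has a general line giving a t-test or Mann–Whitney U test for continuous variables, but does not tie it to STAI.

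The sample size of 65 per group at 95% power is "Based on prior SFR data", that is, on stone-free rate, a secondary outcome. No power, SD, effect size or event rate is given for the stress outcome.

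**The concern.** The primary objective (Section 2) concerns the impact of scope diameter on surgeon stress. The sign of the change can show whether rises are more frequent with one scope, but not how much stress differs. It also gives a 1-point movement full weight as an event, so some events will reflect ordinary score variation.

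Discarding the size of the change generally lowers power when scores are roughly normal. Because the trial was sized on another outcome, no margin has been shown that would absorb this loss. A null result on the primary outcome would then be hard to read: it could mean no difference, or a moderate difference that the sign alone could not detect.

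**Working it through.** **The plan's own figure.** The 65 per group cannot be reproduced, because Section 9 does not give the two stone-free rates. It is compatible with plausible pairs. For 70% against 93.9%, two-sided alpha 0.05, power 95%, pooled formula without continuity correction:

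n = [1.96·√(2·0.8195·0.1805) + 1.645·√(0.70·0.30 + 0.939·0.061)]² / 0.239² = (1.066 + 0.850)² / 0.0571 ≈ 64.3, so 65.

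80% against 99% also gives 65. The figure is not shown to be wrong, but it says nothing about power for stress.

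**Inputs for the stress outcome.** From the documents: 65 per arm, 1:1 allocation, alpha 0.05 (taken as two-sided), event defined as change > 0. Assumed, because the documents are silent: whole-number scores, normal with SD 8 before and after; true caliber effect 4 or 3 points; pre-post correlation r of 0.4, 0.6 or 0.8; no average change in the reference arm; independent procedures; no dropout.

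**Closed form at r = 0.4, 4-point effect.**

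- SD of change = 8·√(2·(1 − 0.4)) = 8.76.
- Binary: with whole-number scores, change > 0 means change ≥ 1, so the cut is at 0.5. Reference arm: 1 − Φ(0.5/8.76) = 0.477. Other arm, 4 points lower: 1 − Φ(4.5/8.76) = 0.304. Pooled proportion 0.391; null SE = √(2·0.391·0.609/65) = 0.0856; alternative SE = 0.0842. Power = Φ[(0.1735 − 1.96·0.0856)/0.0842] ≈ 53%.
- t-test on change: d = 4/8.76 = 0.456; noncentrality = 0.456·√(65/2) = 2.60; power ≈ 73%.
- ANCOVA: residual SD = 8·√(1 − 0.4²) = 7.33; d = 0.546; noncentrality = 3.11; power ≈ 87% (86% in simulation).

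**Simulation (4,000 replicates, rounded scores).** Power:

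| Effect | r | Chi-square on change > 0 | ANCOVA | Total gap |
|---|---|---|---|---|
| 4 | 0.4 | 53% | 86% | 33 |
| 4 | 0.6 | 72% | 94% | 22 |
| 4 | 0.8 | 94% | >99% | about 5 |
| 3 | 0.4 | 33% | 64% | 31 |
| 3 | 0.6 | 45% | 75% | 30 |
| 3 | 0.8 | 76% | 95% | 19 |

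For the 4-point effect, the t-test on change has 73%, 88% and 99% power at r = 0.4, 0.6 and 0.8. At r = 0.4 the gap therefore splits into 73 − 53 = 20 points from dichotomizing and 86 − 73 = 13 points from baseline adjustment. With no true effect, all three tests reject 4–5% of the time.

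**Dependence on the event rate.** At a standardized difference in change of d = 0.5 and 65 per arm, the numeric change has 81% power. The binary outcome, with the cut placed to give the stated average event rate, has:

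| Average event rate | Power | Loss (points) |
|---|---|---|
| 50% | 62% | 20 |
| 30% (or 70%) | 57% | 24 |
| 20% (or 80%) | 50% | 31 |
| 10% (or 90%) | 37% | 44 |

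Losses are taken before rounding.

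**Events with no average change.** From measurement error alone, P(change ≥ 1) = 1 − Φ(0.5/(SEM·√2)), where SEM is the standard error of measurement per administration. An assumed SEM of 1 gives 36% and an SEM of 5 gives 47%. Under the SD 8 model the figure is 46–48%. The assumed range is therefore roughly 36–48%.

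**The case against.** Four points on the other side have force.

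- **Cause and size of the loss.** A reader might infer that the cut at 0 by itself costs 33 points, or that 33 is a ceiling. Neither holds. At r = 0.4, 13 of those points come from baseline adjustment, a separate choice that could also be made with the binary outcome. The gap is small at high correlation with a 4-point effect, and losses above 33 arise when events are rare or very common. The documents supply no SD, correlation, effect or event rate to pick among these.
- **Noise.** A reader might infer that the outcome is dominated by noise. Measurement error is not given, and some of the within-procedure variation in the SD 8 model could be genuine change in stress. The 36–48% range shows what the definition permits, not what happened.
- **Numeric analysis.** A reader might infer that no analysis of the numeric score is planned at all. The general continuous-variable line in Section 9 could cover it. What stands is that no numeric STAI analysis is named as an outcome.
- **Choice of question.** Defining stress as change across the procedure is a legitimate choice. A surgeon who starts anxious and stays there is not flagged by this definition, and ANCOVA would not flag that case either. This is not a defect of the cut.

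The number of surgeons is also not stated. Repeated scores from the same surgeon would alter absolute power for every method above, so these figures are comparisons under independence, not forecasts.

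**Conclusion.** The point holds in a limited form. The primary outcome discards the size of the change, gives no reason for the cut at 0, and is not backed by a named numeric analysis or by adjustment for the pre-procedure score. For roughly normal change scores with about half of procedures showing a rise, and a moderate effect (d near 0.5), dichotomizing costs about 20 points of power at 65 per arm. In the r = 0.4, 4-point scenario, omitting baseline adjustment costs about 13 more. Confidence in the direction of the loss is high. Its size rests on assumed inputs and could be far smaller or larger.

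This does not make the declared outcome invalid: its type I error is sound under the assumptions. Nor does it support replacing the primary test. Section 3 describes enrolment from March to December 2025 as past, so a substitution now would be post hoc.

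**What to change.** Keep the declared binary outcome as primary and state the reason for the cut at 0. Add to Section 9, as the key supporting analysis, an ANCOVA of post-procedure STAI-TX1 on allocated group, with pre-procedure STAI-TX1, stone size and stone location as covariates. Report the adjusted mean difference with its 95% CI. State how many surgeons operated and, if more than one, include a surgeon term.

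State also whether the pre-procedure score was taken before the surgeon knew the allocated scope. If it was not, any anticipatory effect of the scope is already in that score, and both the change and the adjusted difference would leave it out.

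The cost is a few lines of SAP text and one linear model on data already collected. The downside is timing: the analysis must be disclosed as added after enrolment, not presented as prespecified, and reported beside the binary result whichever way the two fall.

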## **8. Data Collection**

Collected variables included:

- Demographics (age, sex, BMI)
- Stone characteristics (size, location, side)
- Operative time
- Perioperative outcomes
- STAI-TX1 scores

## **9. Statistical Analysis (SAP)**

Statistical analyses were performed using SPSS (version 20.0; IBM, Armonk, NY).

- Continuous variables: Student's t-test or Mann–Whitney U test
- Categorical variables: Chi-square or Fisher's Exact test
- Significance level:  $p < 0.05$

Sample size was calculated using G\*Power (v3.1). Based on prior SFR data, 65 patients per group were required (power 95%, alpha 0.05). Multivariable logistic regression analysis was performed to identify independent predictors of stress-related procedures.

Variables included:

- Ureteroscope caliber
- Stone size
- Stone location
- Operative time

Adjusted odds ratios (aOR) with 95% confidence intervals were calculated. Model calibration was assessed using the Hosmer–Lemeshow test.

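### Secondary outcomes get only crude two-group tests, although adjusting for recorded stone size and location would recover precision, mainly for operative time

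*Combined protocol and SAP*

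**What the plan says.** - Section 9, continuous outcomes (operative time): "Continuous variables: Student's t-test or Mann–Whitney U test".
- Section 9, binary and categorical outcomes (stone-free rate, balloon dilation, ureteral injury, JJ stent, complications): "Categorical variables: Chi-square or Fisher's Exact test".
- Section 9, the only adjusted analysis: "Multivariable logistic regression analysis was performed to identify independent predictors of stress-related procedures". Its covariates are caliber, stone size, stone location and operative time. Confidence intervals are mentioned only for the odds ratios from this model.
- Section 8 lists the baseline factors that concern us: "Stone characteristics (size, location, side".
- Section 3 describes allocation: patients were "randomly assigned in a 1:1 ratio using a simple randomization method". No stratification is stated.
- Section 6 lists "Stone-free rate at 1 month" and "Operative time" among the secondary outcomes. Comparing technical outcomes between the two calibers is the first secondary objective in Section 2.
- Section 9 bases the sample size on earlier stone-free-rate data: "65 patients per group were required (power 95%, alpha 0.05".

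**The concern.** The plan treats stone size and location as worth adjusting for when the outcome is surgeon stress. It leaves them out for operative time and stone-free rate, where an effect of stone burden is at least as plausible. Since allocation is not stratified on them, any difference in stone burden between the arms is left to chance, and no planned secondary analysis takes it into account.

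What is at stake is precision and readability. If the covariates are prognostic, the crude comparison of operative time carries variance that recorded data could remove. If the arms happen to differ in stone burden, the reader has no planned estimate that allows for it. The listed tests also promise only p-values for the secondary outcomes, with no effect estimate or interval.

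**Working it through.** **1. The plan's own figure.** The 65 per group cannot be reproduced, because Section 9 gives neither stone-free rates nor sidedness. It can only be bracketed. With the usual two-proportion formula (two-sided 5%, 95% power, no continuity correction),

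n = [1.960·√(2p̄(1−p̄)) + 1.645·√(p₁(1−p₁)+p₂(1−p₂))]² / (p₁−p₂)².

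For 80% vs 99%: p̄ = 0.895, so n = (0.850 + 0.678)² / 0.19² ≈ 65. In the same way, 70% vs 94% gives 64 and 75% vs 96.5% gives 66. Many pairs fit, so no rate can be taken from the plan.

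**2. Chance imbalance.** With 65 per arm, the standardised difference in a baseline covariate has SD √(2/65) = 0.175 and a 95% range of ±1.96 × 0.175 = ±0.34. The probability that it exceeds 0.2 is 2[1 − Φ(0.2/0.175)] = 25%. For a location category with 50% prevalence (assumed), the 95% range of the difference between arms is ±1.96·√(2 × 0.25/65) = ±17 percentage points.

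**3. Operative time.** The documents give no SD, effect size or R². Assume a true difference of 0.4 SD, and let R² be the share of variance (log scale if skewed) explained by stone size and location. Adjustment multiplies the residual SD, and so the CI width, by √(1−R²). The non-centrality is 0.4·√(65/2)/√(1−R²) = 2.280/√(1−R²).

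| R² (assumed) | Non-centrality | Power, normal approximation | Power, t distribution | CI width vs crude |
|---|---|---|---|---|
| 0 | 2.280 | 62.6% | 61.9% | 100% |
| 0.2 | 2.550 | 72.2% | 71.6% | 89% |
| 0.3 | 2.726 | 77.8% | 77.2% | 84% |
| 0.4 | 2.944 | 83.7% | 83.2% | 77% |

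At R² = 0.1 the normal approximation gives 67.1% and a width of 95%.

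**4. Stone-free rate, risk-difference scale.** This was simulated with 1,500 trials per scenario, N = 130, simple randomization and assumed rates of 75% vs 93%. The crude two-proportion test was compared with a linear-model risk difference adjusted for stone size and a binary location, with robust errors.

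| Assumed log-odds (size per SD, location) | Crude power | Adjusted power | SD of estimate, adjusted/crude |
|---|---|---|---|
| 0, 0 | 83.7% | 83.2% | 0.0614/0.0612 = 1.00 |
| 0.7, 0.7 | 82.9% | 85.1% | 0.0599/0.0620 = 0.97 |
| 1.2, 1.0 | 83.5% | 87.3% | 0.0594/0.0631 = 0.94 |

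The gains are 2.2 and 3.8 points. With equal rates of 80% in both arms, the crude test rejected in 4.6% to 4.8% of trials, so it holds its 5% level.

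**5. Stone-free rate, odds-ratio scale.** Logistic models under the same covariate strengths gave an adjusted standard error of the log odds ratio larger than the crude one in every usable fit (median ratio 1.05 and 1.13). Power still rose, from 81% to 83% and from 81% to 88%. A further run gave a median ratio of 1.08 and power of 79% against 84%. The log-odds-ratio interval therefore widens while the estimate moves away from 1. This is the non-collapsibility of the odds ratio.

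**The case against.** The strongest defence is that nothing here is invalid, and that stands. Under randomization the crude differences are unbiased on average, the type I error is held, and chance imbalance is already part of the crude standard error. A reader might infer from the 25% figure that the secondary results are biased or confounded. The documents do not support that. On the assumed R² of 0.2 to 0.4, a 0.2 SD imbalance in stone burden shifts operative time by about 0.2·√R² = 0.09 to 0.13 SD, which is less than one standard error (0.175 SD).

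Three further objections also hold and shape the remedy.

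- The large gain belongs to operative time only. A reader might carry it over to stone-free rate, but the simulated gain there is a few points.
- Adjusted logistic regression does not give narrower odds-ratio intervals, and it replaces a marginal effect with a conditional one. The precision argument for binary outcomes applies on the risk-difference scale.
- Sections 3 and 9 are written in the past tense, with enrolment from March to December 2025. Promoting adjusted models to main results now could be a post hoc switch, with free choice of scale and of location coding.

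Sparse data are also a real limit. At 80% vs 99% there would be about 65 × 0.20 + 65 × 0.01 ≈ 14 failures in all.

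What the defence does not answer is why covariates already chosen for one model should be left out of the operative-time comparison, where using them costs almost nothing.

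**Conclusion.** The point holds as a loss of precision in the secondary analyses. It is not a validity error, and the primary outcome is not affected.

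- **Operative time:** a worthwhile gain, from about 62% to 72–83% power and to 89–77% of the crude CI width. This rests on an assumed 0.4 SD effect, an assumed R² of 0.2 to 0.4 and 65 per arm.
- **Stone-free rate:** a modest gain of about 2 to 5 power points under assumed covariate strengths. On the risk-difference scale it was 2 to 4 points. The logistic test reached 7 points at the strongest setting, but without a narrower odds-ratio interval.
- **Either outcome:** no gain if stone size and location are not prognostic. The documents give no SD, R² or rates from which to settle this.

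**What to change.** 1. **Operative time:** linear regression on allocated caliber, stone size and stone location (log scale if skewed). Report the adjusted difference with a 95% CI.
2. **Stone-free rate, and balloon dilation and JJ stent where events allow:** a covariate-adjusted (standardised) risk difference with a 95% CI, using the same two covariates.
3. **Covariates:** do not copy the stress model's list unchanged. Operative time is measured after allocation and is itself a secondary outcome, so it must not be a covariate here.
4. **Sparse outcomes:** leave ureteral injury and complications unadjusted.
5. **Reporting:** keep the planned crude tests alongside. State whether the adjusted analyses, including the scale for operative time and the coding of stone location, were fixed before the data were seen. If they were not, label them post hoc.

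The cost is a few extra regressions on data already collected, and a coarse coding of stone location, whose categories the plan does not define.

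### The only power figure (95% with 65 per group) rests on stone-free rate, a secondary outcome; no power or detectable difference is stated for the primary outcome, surgeon stress

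*Combined protocol and SAP*

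**What the plan says.** The primary objective in section 2 is "To evaluate the impact of ureterorenoscope diameter on intraoperative surgeon stress during ureterorenoscopy". Section 6 names the primary outcome as "Occurrence of stress-related procedures", a yes/no measure that is positive when the STAI-TX1 change is above zero; section 7 repeats that definition. SFR appears only under the secondary objectives in section 2 and the secondary outcomes in section 6 ("Stone-free rate at 1 month").

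The sample-size basis is in section 9: "Based on prior SFR data, 65 patients per group were required (power 95%, alpha 0.05". The two SFR values, the sidedness of alpha and any allowance for dropout are not given. No section states an expected rate of stress-related procedures, a target difference in that rate, or a power for it.

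**The concern.** A trial's power statement is normally read as applying to its primary hypothesis. Here it belongs to a different outcome, measured on a different scale of rates. A reader who takes 95% as the power for surgeon stress will assume a 5% chance of missing the effect that the trial was meant to find, and may read a non-significant stress result as good evidence that ureteroscope caliber makes no difference. Whether that reading is justified depends on the difference that 65 per group can detect in the stress outcome, and the plan does not say what that is.

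**Working it through.** **Inputs from the documents.** 65 per group, power 95%, alpha 0.05, SFR as the basis, chi-square or Fisher's exact test for categorical variables (section 9); 1:1 allocation (section 3); binary primary outcome (section 6).

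**Assumptions, because the documents are silent.** Two-sided alpha, no continuity correction, 65 analysed in each arm, procedures independent of one another, and a lower-arm stress rate between 10% and 60%.

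**Step 1: the plan's own figure.** With rates p1 and p2, mean rate p̄ and difference d, the size per group is

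n = [1.960·√(2p̄(1−p̄)) + 1.645·√(p1(1−p1) + p2(1−p2))]² / d².

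The SFR rates are not given, so 65 can be neither reproduced nor contradicted. Several pairs fit. For 95% vs 72%, p̄ = 0.835 and n = (1.029 + 0.821)² / 0.23² = 64.7, which rounds up to 65. The pairs 92% vs 67% and 88% vs 61% also give 65.

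**Step 2: difference in the primary outcome detectable at n = 65.** The same equation is solved for d. As a check at a lower-arm rate of 30%, take p2 = 60.8%: p̄ = 0.454 and n = (1.380 + 1.101)² / 0.308² = 64.9, so about 30.8 points are needed.

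| Lower-arm stress rate (assumed) | Points needed, 95% power | Points needed, 80% power |
|---|---|---|
| 10% | 26.0 | 19.4 |
| 20% | 29.4 | 22.6 |
| 30% | 30.8 | 24.0 |
| 35% | 30.9 | 24.3 |
| 40% | 30.7 | 24.3 |
| 50% | 29.5 | 23.7 |
| 60% | 27.2 | 22.1 |

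About 31 points is the maximum for this test at any rate.

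**Step 3: power for smaller differences.** Power = Φ{[d√65 − 1.960·√(2p̄(1−p̄))] / √(p1(1−p1) + p2(1−p2))}. For 30% vs 50%: (1.612 − 1.358) / 0.678 = 0.375, so power is 65%. For 40% vs 55%: (1.209 − 1.384) / 0.698 = −0.250, so power is 40%.

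| Lower-arm rate | 10 points | 15 points | 20 points |
|---|---|---|---|
| 30% | 22% | 42% | 65% |
| 40% | 21% | 40% | 63% |
| 50% | 21% | 41% | 65% |

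**Step 4: sensitivity to the assumptions, at 95% power.**
- If the standard-caliber rate is 20%, 25% or 30% and the thin scope lowers it, the differences needed are 19.0, 21.6 and 23.8 points.
- With Fisher's exact test, about 27.5 to 33 points are needed for lower-arm rates of 10–60%.
- With one-sided alpha 0.05, about 23 to 28 points are needed.

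**The case against.** Five objections deserve an answer.

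- **The basis is disclosed.** Section 9 says openly that the calculation used SFR data, so a careful reader is not misled. That is true, but the section neither warns that the 95% does not carry over to the primary outcome nor gives a figure that does.
- **The 26–31 range is conditional.** This stands. The documents give no stress rate, do not state sidedness, allow Fisher's exact test, and report neither the number analysed nor the number of surgeons. If the same surgeon's procedures are correlated, the effective sample size could change. What needs no assumption is the mismatch itself.
- **The trial is not weak across the board.** This also stands. A reader might infer that the trial would probably miss any moderate effect. Power is below one half only up to about 15 points at mid-range rates; at 20 points it is 63–65%. With a 10% lower-arm rate, 15 points has 62% power and 20 points 82%. At the conventional medium effect, h = 0.5, the approximation gives 0.5·√(65/2) − 1.960 = 0.89, or about 81% power.
- **SFR may be adequately powered.** A reader might infer that SFR is underpowered too, or that the difference behind 65 was implausibly large. The documents give no SFR values and so cannot support either reading.
- **Enrolment is described as finished.** Section 3 reports enrolment from March to December 2025, so the sample size is fixed. That limits the remedy to wording, but not the need for it: the issue is how a null primary result will be read.

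Section 9 does provide 95% confidence intervals for the adjusted odds ratios in the model of stress-related procedures. This helps, but the plan makes no commitment on how a non-significant result will be interpreted.

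**Conclusion.** The point holds as a mismatch between the primary outcome and the basis of the sample size. The plan's single power figure applies to a secondary outcome, and the primary outcome has none. That conclusion follows from sections 2, 6 and 9 alone.

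Its size is conditional. Under the assumptions listed in the working, 65 per group gives 95% power for differences of about 26–31 points and 80% power for about 19–24 points. The requirement is smaller at more extreme rates and somewhat larger with Fisher's exact test. A true difference of 15 points at mid-range rates would be missed about 60% of the time (100% − 40% to 42%), against the 5% that the stated power suggests.

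A reader might go further and call the 65 an arithmetic mistake. The documents do not support that: without the SFR inputs the figure cannot be checked, and plausible pairs reproduce it. Nor does the mismatch bias the estimated effect; it matters most if the primary result is not significant.

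**What to change.** Amend section 9 in three places.

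1. State that the 95% power applies only to the SFR comparison, and give the two SFR rates and the sidedness of alpha used in the calculation.
2. Add the detectable difference for the primary outcome at 65 per group, with its assumptions. For example: about 24 points at 80% power and about 31 points at 95% power if the lower-arm stress rate is 30–40% (two-sided 0.05, uncorrected chi-square, independent procedures). This depends on the group size and assumed rates, not on the observed result, so it is not a post-hoc observed power.
3. Commit to reporting the between-group difference in the primary outcome with its 95% CI, and to interpreting a non-significant result through that interval rather than as absence of effect.

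The change is to wording only. It makes the stated power less favourable for the primary outcome and needs no extra patients.
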